5.4.4. Additional Safety Assessments

5.4.4.1. Clinical Laboratory Tests

Clinical laboratory tests will be displayed for the participants included in the safety analysis set.

The clinical laboratory parameters to be evaluated by the central laboratory include but are not limited to:

• Hematology: basophils, eosinophils, hemoglobin, hematocrit, lymphocytes, monocytes, neutrophils, platelets, red blood cell (RBC) count and white blood cell (WBC) count

• Clinical chemistry: albumin, alkaline phosphatase, alanine aminotransferase (serum glutamate pyruvate transaminase) [ALT (SGPT)], aspartate aminotransferase (serum glutamic oxaloacetic transaminase) [AST (SGOT)], bicarbonate, blood urea nitrogen (BUN), calcium, chloride, creatinine, glucose, potassium, sodium, total bilirubin, and total protein

Due to the Major Disruption resulting from the conflict involving Ukraine and neighboring countries/territories beginning 24 February 2022, central labs were unavailable for some sites over a period of time. In these instances, local labs, limited to the following parameters, may have been entered into the eCRFs: sodium, potassium, chloride, bicarbonate, BUN, creatinine, total bilirubin, direct bilirubin (conditionally), indirect bilirubin (conditionally), AST, ALT, gamma-glutamyltransferase (GGT), alkaline phosphatase (ALP), and LDH. Certain analyses will use central lab data only, while other analyses may use a combination of central lab data and local lab data.

Descriptive statistics and graphical displays of observed values and changes from baseline will be presented for selected chemistry and hematology laboratory tests at scheduled time points. Only central lab data will be used for this analysis.

Shift tables from baseline to post-baseline will be produced for select laboratory parameters. Both central and local lab data will be used for this analysis.

Abnormality criteria based on toxicity grade will be applied to baseline and post-baseline values using National Cancer Institute's Common Terminology Criteria for Adverse Events (NCI-CTCAE) for parameters with NCI-CTCAE criteria defined (Appendix 9). Applicable laboratory results will be graded according to NCI-CTCAE version 5.0. Both central and local lab data will be used for this analysis. Abnormality for selected chemistry and hematology laboratory tests will be summarized by study intervention for:

- Number and percent of participants with post-baseline values by maximum toxicity grade
- Listings of participants with any post-baseline lab value of NCI-CTCAE toxicity Grade 3 or higher

Number and percent of participants with post-baseline elevated liver chemistry tests will also be produced using both central and local lab data, for:

ALT categories

- >1x to <3x Upper limit of normal (ULN)
- $>3 \times \text{ to } <5 \times \text{ULN}$
- $>5 \times \text{ to } < 8 \times \text{ULN}$
- ≥8×ULN

AST categories

- $>1 \times \text{to} < 3 \times \text{ULN}$
- $>3 \times \text{ to } <5 \times \text{ULN}$

- \geq 5× to <8×ULN
- >8×ULN

Total Bilirubin categories:

- $>1 \times \text{to} < 2 \times \text{ULN}$
- ≥2×ULN

ALP categories:

- $>1 \times$ to $<2 \times$ ULN
- $>2\times$ to $<4\times$ ULN
- ≥4×ULN

Both central and local lab data will be used for this analysis.

Number and percent of participants who met each of the following 5 liver function biochemical criteria individually, as well as overall (ie, met any of the 5), as determined by the investigator, will be summarized:

• ALT or AST absolute:

ALT or AST ≥8×ULN

• ALT or AST increase:

ALT or AST \geq 5×ULN but <8×ULN persists for \geq 2 weeks, OR

ALT or AST $\ge 3 \times ULN$ but $< 5 \times ULN$ persists for ≥ 4 weeks

• ALT/AST/Bilirubin or ALT/AST/INR:

ALT or AST $\geq 3 \times ULN$ and total bilirubin $\geq 2 \times ULN$, OR

ALT or AST ≥3×ULN and INR >1.5

• Cannot monitor:

ALT or AST \geq 5×ULN but \leq 8×ULN and cannot be monitored weekly for \geq 2 weeks, OR

ALT or AST $\ge 3 \times ULN$ but $< 5 \times ULN$ and cannot be monitored weekly for ≥ 4 weeks

• Symptomatic:

ALT or AST $\ge 3 \times ULN$ associated with symptoms (new or worsening) believed to be related to liver injury or hypersensitivity

Listings of participants meeting ANY biochemical criteria of post-baseline ALT≥3x ULN, AST≥3x ULN, ALP≥2x ULN, OR total bilirubin≥2x ULN will be created. Additionally, participants will be assessed for the following 2 Combined Biochemical Criteria:

- 1) Total bilirubin $\ge 2xULN$ within 5 days after either ALT or AST $\ge 3xULN$.
- 2) INR >1.5 within 5 days after either ALT or AST $\geq 3xULN$.

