1.3. Schedule of Activities (SoA)

Through Week 52

Phase	Screening		Bli	inded P	lacebo	-contro	lled ^b			Bli	nded A	Active-	contro	lled ^b	
Week	Screening a	0 °	4	8	12	16	20	24	28	32	36	40	44	48	52
Study Procedures d															
Screening/Administrative															
Informed Consent (ICF/eICF e)	X														
Review of Inclusion/Exclusion Criteria	X	X													
Demography/Medical History	X														
Pre-planned Surgery/Procedure(s)	X														
Pre-study Therapy Review for Eligibility	X	X													
Pelvic X-ray	X^f														
Study Intervention Administration															
Randomization		X													
Study Intervention		X	X	X g	X g	X g	X g	X g	X g	X g	X g	X g	X g	X g	X g
Safety Assessments															
Physical Examination (including skin)	X							X							X
eC-SSRS h	X	X	X	X	X	X	X	X	X	X h	X	X h	X	X h	X
Vital Signs i	X	X	X	X	X	X	X	X	X	X i	X	X i	X	X i	X
Height		X													
Weight		X						X							X
Local 12-lead ECG j		\mathbf{X}^{j}													
Tuberculosis Evaluation k	X	X	X	X	X	X	X	X	X	X	X	X	X	X	X
Chest Radiograph ¹	X														
Pregnancy Test ^m	X	X	X	X	X	X	X	X	X	X	X	X	X	X	X
Injection Site Reaction		X	X	X	X	X	X	X	X	X	X	X	X	X	

Phase	Screening		Blinded Placebo-controlled b					Bli	nded A	Active-	contro	lled ^b			
Week	Screening a	0 °	4	8	12	16	20	24	28	32	36	40	44	48	52
Study Procedures d															
Screening/Administrative															
Early Escape						X n									
Efficacy Assessments															
Joint Assessments o	X	X	X	X	X	X	X	X	X		X		X		X
HAQ-DI ^p		X	X	X	X	X	X	X	X		X		X		X
Physician Global Assessment of Disease Activity °		X	X	X	X	X	X	X	X		X		X		X
Patient's Global Assessment of Disease Activity (Arthritis) ^p		X	X	X	X	X	X	X	X		X		X		X
Patient's Global Assessment of Disease Activity (Arthritis and Psoriasis) ^p		X	X	X	X	X	X	X	X		X		X		x
Patient's Assessment of Pain P		X	X	X	X	X	X	X	X		X		X		X
Dactylitis assessments		X	X	X		X		X	X		X		X		X
Enthesitis assessments (LEI, SPARCC)		X	X	X		X		X	X		X		X		X
BASDAI f,p,q		X		X		X		X							X
PsAID-12 p		X		X		X		X							X
FACIT-fatigue ^p		X		X		X		X							X
PROMIS-29 p		X		X		X		X							X
SF-36 ^p		X		X		X		X							X
BSA % Involvement of Psoriasis		X													
IGA-Psoriasis		X				X		X							X
PASI		X				X		X							X
Clinical Laboratory Tests															
QuantiFERON-TB test r	X														
Hepatitis B and C Serologies s	X														
HIV Antibody Test s	X														
Hematology, Chemistry s	X	X	X	X	X	X	X	X	X		X		X		X
Lipid Panel s		X													X

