- d. If a participant discontinues study drug intervention prior to the Week 24 visit, they should be encouraged to return for all remaining study visits through Week 24. The participant should also return for a final safety visit to perform assessments under the Week 112/final safety visit approximately 12 weeks after the last study intervention administration. If a participant permanently discontinues study intervention administration at or after the Week 24 and before the Week 100 visit, the final efficacy visit should occur at the time of discontinuation or as soon as possible and all assessments under the Week 100/final efficacy visit should be performed. Fasting is not required for the final efficacy visit. The participant should also return for a final safety visit to perform assessments under the Week 112/final safety visit approximately 12 weeks after the last study intervention administration.
- e. Must be signed before first study-related activity.
- f. Participants with spondylitis with peripheral arthritis as their primary arthritic presentation of PsA will have confirmation of sacroilitis during screening by a centrally read pelvic X-ray (ie, anteroposterior views of the sacrum). An existing X-ray done within 3 months of screening may be sent for central reading in lieu

- of a screening X-ray (and if not of sufficient quality, a new screening X-ray would then be performed and centrally read). Participants who have confirmed sacroiliitis will complete the BASDAI at specified visits in the SoA.
- g. Study intervention will be administered SC q4w by a healthcare professional during visits to the site until the participant (or caregiver) is trained for self-administration. Study intervention will be administered by site personnel at Weeks 0 and 4. Beginning at Week 8, at the discretion of the investigator and participant, and after appropriate and documented training, participants (or caregiver) may administer study intervention at the investigative site under the supervision of a health care professional. After appropriate training, beginning at Week 32, participants (or caregiver) may administer study intervention at home and on-site visits are only required at Weeks 36, 44, and 52. Safety and efficacy assessments, including blood samples for clinical laboratory and pharmacokinetics/immunogenicity, as specified in the SoA should be performed prior to study intervention administration.

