Phase		Blinded Active-controlled effica- visit								Final efficacy visit ^b	Safety follow- up ^b		
Week	56	60	64	68	72	76	80	84	88	92	96	100	112
Study Procedures a													
IGA-Psoriasis						X						X	
PASI						X						X	
Clinical Laboratory Tests													
Hematology, Chemistry i				X		X		X				X	X
Lipid Panel												X	
C-reactive Protein				X		X		X				X	
PK/Antibodies/Biomarkers													
PK sampling j						X						X	X
Antibodies to study agent j						X						X	X
Serum biomarkers												X	
Plasma biomarkers												X	
Whole Blood (RNA)												X	
PBMC k												X	
Ongoing													
Device deficiencies	X	XX											
Prior and Concomitant therapy	X	XX						X					
Adverse events	X											X	X

- a. After Week 24, study visits will have a visit window of \pm 7 days. Week 112 or the final safety visit (12 weeks after the last dose in participants who discontinued study treatment) will have a visit window of \pm 14 days.
- b. If a participant discontinues study drug intervention prior to the Week 100 visit, they should be encouraged to return for all remaining study visits through Week 100. The participant should also return for a final safety visit to perform assessments under the Week 112/final safety visit approximately 12 weeks after the last study intervention administration. If a participant permanently discontinues study intervention administration before the Week 100 visit, the final efficacy visit should occur at the time of discontinuation or as soon as possible and all assessments under the Week 100/final efficacy visit should be performed. Fasting is not required for the final efficacy visit. The participant should also return for a final safety visit to perform assessments under the Week 112/final safety visit approximately 12 weeks after the last study intervention administration.
- c. Participants (or caregiver) may administer study intervention at home and on-site visits are only required at Weeks 68, 76, 84 and 100. Safety and efficacy assessments, including blood samples for clinical laboratory and pharmacokinetics/immunogenicity, as specified in the SoA should be performed prior to study intervention administration.

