2.2.1.1.3. Safety results

Refer to the latest version of the guselkumab IB for detailed safety results of PSA3001 and PSA3002.

Overall, the guselkumab safety profile in the PsA population was generally comparable with that established in the psoriasis population.

Through 1 year, the pooled safety data from PSA3001 (through Week 60) and PSA 3002 (through Week 52) indicated that both guselkumab dose regimens (ie, 100 mg SC administered at Weeks 0 and 4 and then q8w or q4w) were well tolerated in participants with active PsA. Similar proportions of participants in the guselkumab q8w and q4w groups experienced adverse events (AEs), serious adverse events (SAEs), AEs leading to study discontinuation, AEs with severe intensity, infections, serious infections, and injection-site reactions through 1 year of follow-up. Frequencies of events of suicidal ideation, malignancy, and major adverse cardiovascular events were low and comparable in the guselkumab q8w and q4w groups. There were no events of opportunistic infections, active tuberculosis (TB), anaphylaxis or serum sickness reactions, or suicidal behavior or self-injurious behavior without suicidal intent in guselkumab-treated participants in either of the PSA3001 or PSA3002 studies through 1 year. The proportion of participants experiencing increases in transaminases was slightly higher in the guselkumab q4w group compared with the g8w group. In addition, the number of participants with AEs, SAEs, AEs leading to discontinuation of study intervention, infections, and serious infections per 100 subject-years of follow-up were generally comparable between the guselkumab 100 mg q8w and q4w groups through 1 year and the placebo-controlled period through Week 24.

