At Week 16, all participants in Groups I, II, and III with <20% improvement from baseline in both tender and swollen joint counts will qualify for early escape and will be allowed to initiate or increase the dose of one of the permitted concomitant medications up to the maximum allowed dose as specified in Table 3, as selected by the investigator.

At Week 24, all participants in the placebo group (Group III) will cross over in a blinded fashion to receive guselkumab 100 mg SC q4w through Week 100; this will allow for collection of additional safety data for the guselkumab 100 mg SC q4w dose. Participants in the guselkumab groups (Groups I and II) will remain on the dosing regimen they were randomized to at Week 0, through Week 100.

Database locks (DBLs) are scheduled at Week 24, Week 52 and the end of the study (Week 112). The first DBL will occur when all randomized participants have either completed the Week 24 assessments or terminated study participation prior to the Week 24 visit (referred to as Week 24 DBL). The second DBL will occur when all randomized participants have either completed the Week 52 assessments or terminated study participation prior to the Week 52 visit (referred to as Week 52 DBL). The third DBL will occur when all participants have either completed their final safety visit or have terminated study participation (referred to as Final DBL).

The end of study is considered as the last visit for the last participant in the study.

A diagram of the study design is provided in Section 1.2, Schema.

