- 2. Placebo → Guselkumab 100 mg q4w: Participants who started treatment with placebo and later received treatment with guselkumab (due to CO or inadvertently). Follow-up will start from the first dose of guselkumab up to end of study. All the safety events/measurements that occurred on and after the first dose of guselkumab up to end of study will be included in this group.
- 3. **Guselkumab 100 mg at Weeks 0, 4, and then q8w**: Participants who received guselkumab 100 mg q8w prior to Week 24 with an additional dose at Week 4. Follow-up will be from the first dose up to Week 52.
- 4. **Guselkumab 100 mg q4w**: Participants who received guselkumab 100 mg q4w prior to Week 24. Follow-up will be from the first dose up to end of study.
- 5. **Guselkumab 100 mg q4w Combined:** Participants in Groups 2 and 4.
- 6. All Guselkumab Combined: Participants in Groups 2, 3, and 4.

The above intervention groups 1-2 are **not mutually exclusive**. The safety tables will have the column headings below:

	Guselkumab					
		Placebo				
	\rightarrow 100			100 mg q4w	All	
	Placebo	100 mg q4w	100 mg q8w	100 mg q4w	Combined	Combined
Analysis set: Safety Analysis Set	###	###	###	###	###	###

CONFIDENTIAL – FOIA Exemptions Apply in U.S.

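### In the Week 52 and end-of-study laboratory tables, the crossover and q4w Combined columns can understate short-lived abnormalities, because early q4w exposure has 4 scheduled draws after crossover and 7 in randomised q4w

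*SAP*

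**What the plan says.** The laboratory schedule is in Protocol 1.3. The row "Hematology, Chemistry s" has post-baseline draws at Weeks 4, 8, 12, 16, 20, 24, 28, 36, 44 and 52. The long-term row "Hematology, Chemistry i" has draws at Weeks 68, 76, 84, 100 and 112. The thinning follows the move to home dosing: after Week 28, "on-site visits are only required at Weeks 36, 44, and 52", and in the second year "on-site visits are only required at Weeks 68, 76, 84 and 100". Samples are taken before dosing, so the Week 24 draw in Group III precedes its first guselkumab dose.

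SAP 5.4.1 defines the columns. For the crossover column from Week 52 on, "All the safety events/measurements that occurred on and after the first dose of guselkumab up to end of study will be included in this group". The q4w Combined column adds these participants to randomised q4w.

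SAP 5.4.4.1 tabulates "Number and percent of participants with post-baseline values by maximum toxicity grade" and the number and percent in each ALT, AST, bilirubin and ALP category. SAP 5.4.3 promises average weeks of follow-up for the adverse-event tables. SAP 5.4.4.1 makes no such promise for laboratory tables and plans no count of draws.

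**The concern.** A laboratory abnormality is counted only if blood is drawn while it is present. Participants who cross over at Week 24 start q4w just before the schedule thins from 4-weekly to 8-weekly, so their early exposure is observed less often than the same exposure in randomised q4w. The planned percentages do not reveal this.

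Protocol 4.1 gives as the purpose of assigning q4w at crossover that "this will allow for collection of additional safety data for the guselkumab 100 mg SC q4w dose". On liver enzymes, Protocol 2.2.1.1.3 reports from the earlier studies that "The proportion of participants experiencing increases in transaminases was slightly higher in the guselkumab q4w group" than on q8w. Protocol Table 1 describes the q4w association as mild, up to 3 times the upper limit of normal. Increased monitoring in Protocol Appendix 10.8 starts at ALT or AST of 3 times that limit, so milder rises depend mainly on scheduled draws. A lower percentage in the crossover or q4w Combined column could be read as reassurance when part of it reflects fewer samples.

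**Working it through.** The plan states no figure for this, so there is none to reproduce. The check counts draws and then computes the chance of catching one episode.

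**Inputs.** Draw weeks come from Protocol 1.3. Group III starts guselkumab at Week 24 (Protocol 4.1). Planned group size is 150 per arm. Episode duration D is an assumption. Unscheduled tests and dropout are ignored.

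**Draws in the first 28 weeks on q4w**
- Randomised q4w: Weeks 4, 8, 12, 16, 20, 24, 28, which is 7 draws with gaps of 4 weeks each.
- Crossover: calendar Weeks 28, 36, 44, 52, which are 4, 12, 20 and 28 weeks since first dose. That is 4 draws with gaps of 4, 8, 8, 8.
- In the first 24 weeks the counts are 6 and 3.

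**Detection.** For one episode of D weeks with onset uniform over T weeks, the share containing a draw is the sum over gaps of min(D, gap), divided by T. Here T = 28.

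| D (weeks) | Randomised q4w | Crossover | Ratio | Equal-size q4w Combined, ratio to randomised |
|---|---|---|---|---|
| 2 | 7×2/28 = 50% | 4×2/28 = 29% | 0.57 | 0.79 |
| 4 | 7×4/28 = 100% | 4×4/28 = 57% | 0.57 | 0.79 |
| 6 | 28/28 = 100% | (4+3×6)/28 = 79% | 0.79 | 0.89 |
| 8 or more | 100% | (4+3×8)/28 = 100% | 1.00 | 1.00 |

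**Full columns, D = 4**
- Through Week 52: randomised 40/52 = 77%, crossover 16/28 = 57%, ratio 0.74.
- Through Week 112: randomised 60/112 = 54%, crossover 36/88 = 41%, ratio 0.76.
- At Week 112 the ratio rises to 0.94 for D = 8 and 1.00 for D = 16.

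**Percentage of participants.** The tables count participants, not episodes. If a true proportion p has at least one episode in 28 weeks, and episodes follow a Poisson process with detection d, the observed proportion is 1 − (1 − p)^d. With p = 30% and D = 4, randomised q4w shows 30% and crossover shows 1 − 0.7^0.571 = 18.4%. With p = 10%, the figures are 10.0% and 5.8%. The values of p are illustrations only.

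**Follow-up time.** Through Week 52 there are 10 draws in 52 weeks (0.77 per 4 weeks) against 4 in 28 weeks (0.57 per 4 weeks), a ratio of 1.35. For abnormalities of 4 weeks or less, dividing by follow-up would therefore not restore comparability. The SAP plans no such rate for laboratory data.

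**The case against.** The strongest reply is that the size rests wholly on D. Through Week 52 no gap exceeds 8 weeks, so an abnormality lasting 8 weeks or more meets a scheduled draw in every column, and the documents do not say how long these abnormalities last. That stands, and the point is conditional on it. Shorter durations are not fanciful, though: the SAP's own liver criteria use persistence of 2 and 4 weeks.

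The SAP also plans by-visit summaries of observed values and changes, which do not depend on cumulative draws. It lists individuals with Grade 3 or higher values and with ALT or AST at 3 times the upper limit or more. No formal safety comparison is planned. All of this is true and limits the harm, but the listings do not cover mild transaminase rises, and the pooled percentages remain.

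A reader might infer three stronger things that the documents do not support:
- **That the controlled comparison with placebo is biased.** Through Week 24 all arms share the same six draws, so those tables are equally sampled.
- **That thinning after Week 28 singles out these two columns.** It applies to every arm. Only the sparse sampling of early exposure is specific to crossover.
- **That the placebo column is unfairly set against sparsely sampled active columns.** Randomised q4w and q8w keep all six placebo-period draws and add more, and an ever-reached percentage cannot fall when draws are added.

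**Conclusion.** The point holds for the Week 52 and end-of-study tables and for abnormalities shorter than the gap between draws: under 8 weeks through Week 52, under 16 weeks afterwards. In the first 28 weeks of exposure the crossover group would show 0.57 of the episodes seen in randomised q4w for durations up to 4 weeks, 0.79 at 6 weeks, and the same from 8 weeks. An equal-size q4w Combined column would show 0.79, 0.89 and 1.00. These figures assume a single episode with uniform onset, full attendance and no unscheduled tests. The real size is unknown because the durations are unknown.

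The crossover group's shorter follow-up (28 against 52 weeks, then 88 against 112) also lowers its crude percentages. That is a separate cause and should not be confused with this one. It would be going too far to say that the tables will understate q4w liver effects; they can, under the stated condition, and as planned a reader could not tell.

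**What to change.** In SAP 5.4.4.1:

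1. Add to the Week 52 and end-of-study outputs a supplementary table of maximum toxicity grade and liver categories for crossover, randomised q4w and q4w Combined. Restrict it to scheduled draws at 4, 12, 20 and 28 weeks since first guselkumab dose, which are calendar Weeks 4, 12, 20, 28 for randomised q4w and 28, 36, 44, 52 for crossover. Exclude unscheduled tests from this table. Both groups then have 4 scheduled draws over 28 weeks.
2. Show the number of draws and the follow-up per column in all laboratory tables.
3. Keep the planned tables.
4. Make any split by period on time since first guselkumab dose. A calendar split at Weeks 0 to 28 would leave the crossover group one on-drug draw against seven and recreate the mismatch.

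The cost is SAP wording, one table shell and extra rows in existing shells, with no new data. The downside is small: the matched table sets aside three of the seven early randomised q4w draws (Weeks 8, 16 and 24), which remain in the planned tables.
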